#### **C. Vital Signs**

Vital signs will be performed at baseline, during and within 15 min post-transfusion, 1 Day post-transfusion, and 7 Days post-transfusion. Vital signs include temperature, heart rate (HR), respiratory rate (RR), blood pressure (BP), and arterial oxygen saturation via pulse oximetry (SpO2), will be listed by treatment sequence, treatment group and time point. Vital signs will be summarized as actual and change from baseline for each treatment group at each scheduled assessment.

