14.3.1 Prior to Each Transfusion Episode

Blood Product Procedures

1. Collect specimen from each unit prior to the transfusion (Section 16.1)
 - a. Local: Complete Blood Count (CBC)
 - b. Central: supernatant potassium, supernatant sodium, and supernatant hemoglobin

Subject Procedures

1. Measure weight
2. Conduct physical examination (only prior to the first transfusion of Treatment Period 2)

- a. Perform an abbreviated physical examination, including examination of general appearance, eyes/ears/nose/throat, pulmonary/chest, cardiovascular, abdominal, and neurological
3. Record vital signs within 1 hour prior to transfusion. Vital signs include HR, BP, RR, SpO₂, and temperature
4. Local Laboratory Tests (may be collected/tested at any time within 5 days before the transfusion unless otherwise noted)
 - a. Prior to Treatment Period 2 only: Serum or urine pregnancy test; not required if female subjects are not of child-bearing potential (ie, prior to menses onset, surgically sterilized, 1-year postmenopausal)
 - b. Routine blood typing and crossmatch per site standard practice
 - c. RBC antibody screen
 - o If positive, conduct RBC antibody identification and record only new RBC antibodies, if applicable
 - d. Crossmatch with RBCs derived from Mirasol-treated WB if the previous study transfusion was a MIR RBC product
 - e. CBC, plasma free hemoglobin; and haptoglobin within 1 hour prior to transfusion (Section 16.2.1)
 - f. Chemistry within 1 hour prior to transfusion (Section 16.2.1)
5. Collect blood from subject for Central Laboratory Tests (Section 16.2.2)
 - a. Collect and hold blood sample for RBC antibody testing, when the antibody screen and crossmatch performed at the local lab either is positive for an antibody specific to MIR-treated RBCs or inconclusive. See Section 16.2.2.1 for details regarding criteria for sending samples to the central laboratory
 - b. Collect blood sample for HLA testing, only during Treatment Period 1 (Section 16.2.2.2)
6. Record all concomitant medications taken starting from the day of the first study transfusion and throughout the study, including all blood products transfused (eg, off-protocol RBCs, platelets) (Section 17)
7. Record AEs, SAEs, and UADEs (Section 19). All AEs will be recorded from the time of the first study transfusion through the final follow-up or early termination visit

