Post-transfusion purpura	
 • Destruction of PLTs (thrombocytopenia) in a patient with history of sensitization, occurring 7-10 days after transfusion.
Transfusion-associated graft-versus-host disease	
 • Occurs when viable T lymphocytes in the transfused component react against recipient tissue antigens. • Immunocompromised patients are at greatest risk.
Transfusion-transmitted infection	
 • Characterized by laboratory testing evidence of pathogen (ie, viruses, bacteria, parasites, variant Creutzfeldt-Jakob disease agent) in the transfusion recipient. • Occurs despite donor screening and blood testing.
Hypotensive transfusion reactions	
 • Hypotension occurs during or within 1 hour of transfusion. • Characterized in adults by SBP ≤ 80 mmHg and SBP decrease ≥ 30 mmHg. • Characterized in children by SBP decrease $> 25\%$ from baseline.
Transfusion-associated dyspnea	
 • Acute respiratory distress within 24 hours of transfusion, not attributable to allergic reaction, TACO, or TRALI.

Adverse Reactions	Description
Adverse Reactions Specific to Red Blood Cell Transfusion	
Hemolytic transfusion reaction	
• Immunologic destruction of transfused RBCs, resulting from preformed antibodies to incompatible transfusion product (1:76,000) or ABO incompatibility (1:40,000).
Alloimmunization	
• Characterized by clinically significant recipient antibodies to transfused RBC antigens.• May be detected in pretransfusion antibody screening.
Transfusion-associated circulatory overload	
• Chronic anemia patients with increased plasma volumes are at risk of circulatory overload with RBC transfusions.
Iron overload	
• Characterized by significant iron accumulation following multiple RBC transfusion.• Greater risk for patients with decreased RBC production or increased RBC destruction; less risk for patients with hemorrhage.
Nonimmunologic hemolysis	
• RBC lysis resulting from hypotonic fluid exposure, drug effects, bacterial toxins, thermal injury (ie, freezing, overheating), metabolic damage, or mechanical injury/osmotic stress

Source: AABB. Primer of Blood Administration. 2010; AABB, ARC, ABC, ASBP ; and CDC NHSN Hemovigilance Module (Aug 2014)

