21.2 Reporting Conventions and Definitions

Duration of events will be calculated in days as (stop date – start date + 1). Conversions to weeks, months, or years will be calculated as days/7, days/30.4375, or days/365.25, respectively.

For analysis purposes, baseline will be defined as the day of the first transfusion within each treatment period. In general, missing values will be handled as follows. For continuous variables at baseline, missing values will be excluded from calculation of summary statistics and the number and percent of patients with missing values will be displayed. For categorical values at baseline, the number and percent of patients with missing values will be displayed.

Summary tables of post-baseline measures will be presented by treatment:

- MIR RBCs: RBCs will be derived from WB collected in CPD solution, treated with the Mirasol System for WB, LR, and stored in AS-3 for \leq 21 days at 1 - 6°C
- REF RBCs: LR apheresis RBCs or WB-derived RBCs will be per site standard inventory

Patients will be randomized by treatment sequence: MIR RBCs followed by REF RBCs (MR) or REF RBCs followed by MIR RBCs (RM). Summary tables of baseline measures will be presented by treatment sequence.

Treatment start date is defined within each period as the date of the first transfusion received for each period.

Study day for analysis purposes is defined as (date of event – treatment start date) (+ 1 if the event occurs after treatment start date) within each period.

Baseline for analysis purposes is defined as the last assessment prior to treatment start date/time (or randomization date, for patients who never receive any treatment) for each treatment period. In cases where the date is the same and the times are unknown, assessments taken on the same day are considered baseline.

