## **VI. General Analytical Considerations**

### **A. Study Time Points**

#### Baseline

Baseline for analysis purposes is defined as the last assessment prior to treatment start date/time (or randomization date, for patients who never receive any treatment) for each treatment period. In cases where the date is the same and the times are unknown, assessments taken on the same day are considered baseline.

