#### Treatment Start Date

Treatment start date is defined within each period as the date of the first transfusion received for each period.

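### Vital-sign change is measured from the start of the treatment period, so after the first transfusion of a period it mixes the acute transfusion effect with between-visit variation

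*SAP*

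**What the plan says.** SAP IX.C sets the summary: "Vital signs will be summarized as actual and change from baseline for each treatment group at each scheduled assessment". It gives the schedule as: "Vital signs will be performed at baseline, during and within 15 min post-transfusion, 1 Day post-transfusion, and 7 Days post-transfusion". It does not say which baseline is meant.

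SAP VI.A supplies the only definition: "Baseline for analysis purposes is defined as the last assessment prior to treatment start date/time", applied separately to each treatment period. It fixes the anchor with: "Treatment start date is defined within each period as the date of the first transfusion received for each period". Protocol 21.2 carries the same definition. It also has a shorter one, in which "baseline will be defined as the day of the first transfusion within each treatment period". Both tie baseline to the first transfusion of the period.

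Protocol 14.3.1 asks sites to "Record vital signs within 1 hour prior to transfusion". Section 14.3 applies this to every wash-in transfusion and to both endpoint episodes, in both periods. Readings follow at 15 minutes, hourly, at the end of transfusion, 15 minutes after the end (14.3.2) and at 1 day (14.3.3).

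**The concern.** Readings during a transfusion and just after it are suited to showing what that transfusion did. The protocol's descriptions of transfusion reactions are largely about short-term change. In Table 19-1 a febrile reaction is a temperature rise of at least 1°C during or immediately after transfusion. For the hypotensive reaction the table states: "Hypotension occurs during or within 1 hour of transfusion". It adds a systolic fall of at least 30 mmHg in adults, or of more than 25% in children.

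The matching reference is the reading taken shortly before the same transfusion. It is collected, but neither document plans a vital-sign change from it. If the period-start value is subtracted instead, every later change carries weeks of between-visit variation, and a difference between products in acute tolerance becomes harder to see.

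This table also gives a numeric check that does not depend on adverse event reporting. That has some value in a trial whose documents say blinding is not feasible (Protocol 10.1).

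**Working it through.** **Inputs**

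- Wash-in: 50 days from Day 0 of each period, then 2 endpoint episodes (Protocol 10.1).
- Mean transfusion interval: 2 to 4 weeks (Protocol 11.2), taken here as a constant L of 14 to 28 whole days. Constancy is an assumption.
- Screening up to 28 days, and final visit at least 60 days after the last per protocol transfusion (Protocol 10.4).
- Correlations between readings: not in the documents, so assumed.

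**1. Check the timeline against the plan's own figure.** Let t1 = L × ceil(50/L) be the first endpoint transfusion (one falling exactly on day 50 counts), and t2 = t1 + L the second. Period 2 starts at t2 + L. Participation in days = screening (0 to 28) + (t2 + L) + t2 + 60, divided by 30.4375 for months (the conversion in Protocol 21.2).

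| L | t1 | t2 | Days without screening | Months, with 0 to 28 days of screening |
|---|---|---|---|---|
| 14 | 56 | 70 | 84 + 70 + 60 = 214 | 7.0 to 8.0 |
| 21 | 63 | 84 | 105 + 84 + 60 = 249 | 8.2 to 9.1 |
| 24 | 72 | 96 | 120 + 96 + 60 = 276 | 9.1 to 10.0 |
| 28 | 56 | 84 | 112 + 84 + 60 = 256 | 8.4 to 9.3 |

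Over all L the range is 7.0 to 10.0 months. This agrees with the stated participation of about 7 to 9 months, so the timeline is a fair basis.

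**2. Age of the period-start reference when an episode begins, L = 14 to 28.**

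| Episode | Age of reference | Positions over the 15 values of L |
|---|---|---|
| First transfusion of the period | 0 days | 15 |
| Later wash-in transfusions | 14 to 48 days | 29 |
| First endpoint transfusion | 50 to 72 days | 15 |
| Second endpoint transfusion | 68 to 96 days | 15 |

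At the first transfusion of a period the pre-transfusion reading is itself the baseline, so nothing is added. If a transfusion on day 50 were instead counted as wash-in, L = 25 would give endpoint transfusions on days 75 and 100, hence about 96. With a same-episode reference the gap is hours for the during and 15-minute readings, and about 1 day for the Day 1 reading, at every episode.

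**3. Effect on precision.** With equal variance σ² at both readings and correlation ρ, the SD of the change is σ√(2(1 − ρ)). The ratio of the two SDs is √((1 − ρ_weeks)/(1 − ρ_visit)).

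| ρ_visit | ρ_weeks | Ratio |
|---|---|---|
| 0.8 | 0.5 | √(0.5/0.2) = 1.58 |
| 0.8 | 0.6 | √(0.4/0.2) = 1.41 |
| 0.7 | 0.5 | √(0.5/0.3) = 1.29 |
| 0.7 | 0.6 | √(0.4/0.3) = 1.15 |

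The SD is therefore 15% to 58% larger. Over wider assumptions (ρ_visit 0.7 to 0.9, ρ_weeks 0.4 to 0.8, with ρ_weeks below ρ_visit) the ratio runs from 1.15 to 2.45.

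**4. Compare the time points.** The SAP list names baseline and then "during and within 15 min post-transfusion, 1 Day post-transfusion, and 7 Days post-transfusion". Protocol Table 14-1 schedules vital signs at screening, before each transfusion, during and within 15 minutes after it, and at 1 day. It schedules none at 7 days, and neither does Protocol 14.3.4. The SAP list thus has a Day 7 entry with no source in the protocol, and it does not name the pre-transfusion reading.

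**The case against.** **Baseline in IX.C may mean the per-episode reading.** The list follows the per-transfusion columns of Table 14-1, with baseline where the table has the column for readings before transfusion, and SAP IV.E refers to that table for all measurements. This stands as a real ambiguity. It does not remove the point: the defined term says period start, and two programmers could produce different tables. SAP IX.B leans the same way, since its laboratory shifts start from the wash-in pre-transfusion value, whereas Protocol 21.9.2 also planned laboratory change from the pre-transfusion time point between consecutive transfusions.

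**Little is lost.** Much of this stands. Actual values are summarised and every reading is listed. If the scheduled pre-transfusion reading is summarised, the mean acute change can be recovered for the same subjects, because mean(post − base) − mean(pre − base) = mean(post − pre). Its SD cannot be recovered from those summaries. Confirmed transfusion reactions are recorded as adverse events (Protocol 19.6.3) and have their own table (SAP IX.A). The adult hypotension description also includes an absolute level, a systolic pressure of 80 mmHg or less, which actual values would show. No test or margin rests on the vital-sign table.

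**Drift cancels between products.** Drift common to both largely does, because each period has its own baseline. Drift that differs by product would not. Protocol 19.3.3 reports an RBC AUC 16.7% lower with Mirasol treatment, but an effect of this on pre-transfusion vital signs is only an inference, and physicians may adjust volume and frequency.

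**Change from period start has its own use.** It does: it shows cumulative change over repeated exposure. That argues for keeping it beside the within-episode change.

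**Conclusion.** The point holds as a matter of definition and precision. Under the SAP's only definition of baseline, the vital-sign change at every transfusion after the first in a period combines the acute effect with between-visit variation. The reference is then 14 to 48 days old in the wash-in and 50 to about 96 days old at the endpoint episodes. The SD of the change is about 15% to 58% larger than it need be. The ages rest on constant 14 to 28 day intervals. The SD figures rest on assumed correlations and equal variances.

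Three stronger conclusions might be inferred, and the documents do not support them:

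- That all vital-sign changes are taken against a reference 7 weeks old or more. On the timeline above this is so for only 30 of 74 episode positions (41%), and the first transfusion of each period is unaffected.
- That acute reactions would be hidden. They are tabulated as adverse events, and the readings themselves are summarised and listed.
- That the product comparison is biased. Only product-specific drift could do that, and the documents give no evidence of it for vital signs.

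The primary analysis is untouched. The change is still worth making, because the better reference is already collected.

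**What to change.** In SAP IX.C:

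1. Define the acute change, for readings during transfusion, at its end, 15 minutes after it and at Day 1, as the reading minus the value taken within 1 hour before that same transfusion. Summarise it by product and transfusion number.
2. Keep change from period baseline as an additional, separately labelled summary of cumulative change.
3. Add the pre-transfusion reading to the list of time points.
4. Reconcile the Day 7 vital signs with Protocol 14.3.4 and Table 14-1. This is needed whichever baseline was meant.

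The cost is SAP wording and table shells. The first three steps need no new data, because the readings are already part of the protocol schedule.

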#### **D. Physical Examination**

Physical examination will include assessment of general appearance, eyes/ears/nose/throat, pulmonary/chest, cardiovascular, abdominal, and neurological. Physical examination will be captured at baseline and at the end of study treatment follow-up. All examination findings will be listed.

#### **E. Pregnancy Test**

For all females of child-bearing potential, a listing of pregnancy test including test date, test result, and reason if test not taken will be presented.

#### **F. Treatment-Emergent Antibodies**

The number and percentage of subjects with incident treatment-emergent antibodies with confirmed specificity to RBCs derived from Mirasol-treated WB will be presented by time intervals antibodies are detected.

#### **G. HLA Alloimmunization Rates**

HLA alloimmunization rates will be descriptively summarized by treatment.
